### 6.3.5 *Management, Timing and Assessment of SUSARs*

Expedited Notification of SUSAR to the Competent Authorities/IRB
	
The Pharmacovigilance Department of the GEICAM (on behalf of the sponsor) is responsible to notify to each of the competent authorities and IRBs of the participating countries, all the SUSARs collected in the study, following the procedures shown in the current legislation.

Timing of notification
	
The deadline for reporting a SUSAR shall be 15 calendar days from when the Sponsor becomes aware of it. When suspected SUSAR caused the death of the patient or endangered her life, the Sponsor will send the information within 7 calendar days from the date on which it becomes aware. This information must be completed, if possible, in the next 8 days.

Expedited reporting of other relevant safety information
	
Sponsor will also notify, expeditiously, all the information that could modify the balance benefit/risk of the investigational product, or determine changes in its administration pattern or in the study performance, such as:
 
 
○ A qualitative change or an increase in the percentage of occurrence of the SAR expected, which are considered clinically significant.
 
○ The SUSAR occurring after completion of the study and are reported by the investigator to the sponsor.
 

	
 
○ New events related to the conduct of a trial or the development of an IMP likely to affect the safety of patients, such as: 
 
✓ SAE that could be related with the study procedure and could modify the conduct of the trial.
 
✓ A significant risk to patients such as lack of efficacy in a drug used to treat a life-threatening illness.
 
✓ A major safety finding from a newly completed animal study (such as carcinogenicity).
 
✓ A temporary halt of a trial for safety reasons if the trial is conducted with the same investigational medicinal products in another country and if this information is known by Sponsor.
 
✓ Any recommendation of the IDMC that is relevant to the safety of patients (if applicable).
 
 
 
 
This relevant information shall be notified as soon as possible and no later than 15 days after Sponsor becomes aware of it. Additional information will also be notified as quickly as possible.

Annual Safety Reports	
The annual safety reports that include the SAEs and SUSARs collected during the study will be sent by the Sponsor to the Competent Authorities at the time established by the current legislation.

Notification to investigators	
Sponsor will communicate to the investigators any safety information that may affect the safety of trial patients, as soon as possible.
 
Information on SUSAR occurred during the study will be sent at the same time that it is notified to competent authorities but without submitting any information on the treatment arm.
 
They will be informed also, throughout the entire study, of any safety aspect that impacts the performance on the clinical trial or in the product development, including the interruption or modification in the development program of the protocol safety-related.

## 6.4 Efficacy assessments

The following assessments will be performed at baseline, week 3 (day 22 +/- 3 days) and week 12 (day 85 +/- 3 days) or early withdrawal visit.

- Symptoms of vaginal atrophy (vaginal dryness, dyspareunia and pruritus).
- Signs of vaginal atrophy (mucosa with thinning or flattening of folds, dryness or fragility of the vaginal mucosa).
- Measurement of vaginal pH on the vaginal secretion using a reactive strip (pH 2.0 - 9.0, provided by the sponsor). The investigator team will insert the strips in the vagina and will moisten them as much as possible with the vaginal wall secretion. Then, when the strip is coloured, the investigator will check the combination of colours on the strip and check the pH value to which it corresponds, recording this value in the eCRF. The reading should be made whilst the strip is still damp. The strips will be discarded once the pH has been recorded in the eCRF.
- Vaginal cytology sample to evaluate the vaginal Maturation Value. Two smears (with two different spatulas provided by the sponsor one to take the sample and the other to take the countersample) will be made per patient (sample and countersample), which will be obtained from the bottom of the right and left vaginal sac respectively. Each smear will be suitably labelled. The vaginal smears will be fixed whilst they are still moist with a water-soluble fixation spray for cytodiagnosis (provided by the sponsor). The cytologic samples will be sent to central laboratory (full instructions will be given in a laboratory manual). For the cytologic evaluation, the number of parabasal, intermediate and superficial cells will be calculated in duplicate on 100 consecutive cells of vaginal cytology. The average of the two percentages obtained for each cell type will be calculated, which will serve to determine the maturation value (MV) based on the following formula:

$$0.2 \times (\% \text{ parabasal}) + 0.6 \times (\% \text{ intermediate}) + 1.0 \times (\% \text{ superficial}).$$

## 6.5 Impact on sexual function

Patient reported outcomes of health related with the sexual function will be assessed using the **FSFI (Female Sexual Function Index)** (see attachment 4). It was developed for the specific purpose of assessing domains of sexual functioning (e.g. sexual arousal, orgasm, satisfaction, pain) in clinical trials. It is not a measure of sexual experience, knowledge, attitudes, or interpersonal functioning in women. It is not designed for use as a diagnostic instrument and should not be used as a substitute for a complete sex history in clinical evaluation. However, when initial assessment reveals a sexual concern, using the FSFI (or an equivalent set of questions) can help both the physician and the patient measure the nature and severity of the problem as well as identify an appropriate course of treatment.

The FSFI is a brief multidimensional scale with 19-item questionnaire composed of three multi-item functional subscales (sexual activity, sexual intercourse and sexual stimulation).

Patients will complete each questionnaire at baseline, week 3 (day 22 +/- 3 days) and week 12 (day 85 +/- 3 days) or early withdrawal visit.

Completed questionnaires are always considered source document and must be filed accordingly.

Patients must preferably complete these instruments in the hospital and prior to having any tests and to any discussion of their progress with healthcare personnel at the site. Interviewer administration in clinic may be used under special circumstances (eg, patient forgot their glasses or feels too ill).

---

## 7. Data Quality Assurance

To ensure accurate, complete and reliable data, the Sponsor or delegated people on behalf of the sponsor will do the following:

- provide instructional material to the study sites, as appropriate
- sponsor a start-up training session to instruct the investigators and study coordinators. This session will give instructions on the protocol, the completion of the eCRFs, and study procedures
- make periodic visits to the study site to review study progress, investigator and patient compliance with the clinical trial protocol requirements and any emergent problems.
- be available for consultation and stay in contact with the study site personnel by mail, telephone, and/or fax
- review and evaluate eCRF data and use standard computer edits to detect errors in data collection
- conduct a quality review of the database
- verify the quality of the data

To ensure the safety of participants in the study and to ensure accurate, complete, and reliable data, the investigator will keep records of laboratory tests, clinical notes, and patient medical records in the patient files as original source documents for the study. If requested, the investigator will provide GEICAM (on behalf of the sponsor), applicable regulatory agencies, and applicable ethical review boards with direct access to original source documents.

### 7.1 Data Management and Registries file

Data for this study will be recorded via an electronic data capture system using eCRFs. Data will be transcribed by the site from the paper or electronic source documents onto the eCRF. In no case the eCRF is to be considered as source data for this trial. The eCRFs must be completed in an electronic Data Base called ORACLE. That electronic Data Base carries out with the regulatory authorities requirements. It is the responsibility of the Investigator to maintain adequate and accurate eCRFs (according to the technology used) designed by GEICAM (on behalf of the sponsor) to record (according to GEICAM instructions) all observations and other data pertinent to the clinical investigation. All eCRFs should be completed in their entirety in a neat, to ensure accurate interpretation of data.

Should a correction be made, the corrected information will be entered in the eCRF overwriting the initial information and including a reason for the change. An audit trail allows identifying the modification.

Data are available within the server of GEICAM as soon as they are entered in the eCRF.

The computerized handling of the data by GEICAM when available in the eCRF may generate additional requests to which the Investigator is obliged to respond by confirming or modifying the data questioned. The requests with their responses will be managed through the eCRF.

## 8. Sample Size and Statistical Methods

### 8.1 Determination of Sample Size

This is an exploratory study and there are scarce data to allow a precise sample size calculation. The most relevant data come from Pfeiler(16) who reported that the levels of FSH in patients treated with aromatase inhibitors fell from a mean value of 75.7 to 66.0 mIU/ml after two weeks of daily vaginal treatment with 0,5 g of estriol. Although no figures are reported of the variability of those measurements, an estimation of the standard deviation can be made applying the standard rule of  $[sd = \text{range}/4]$ . The reported range of FSH values in that report is 45.6 – 134.6, thus a reasonable approximation to the sd is  $89/4 = 22.3$ . Under these assumptions, it can be calculated that a sample size of 44 would provide 80% power to detect with an  $\alpha=0.05$  a decrease of FSH levels from 75.7 to 66.0 mIU/ml assuming a standard deviation of 22.3.

The hormone levels in women treated with IA who are not receiving estrogen therapy are likely to suffer physiological temporal oscillations. These variations could make difficult the interpretation of any eventual modification of hormone levels observed in the estriol treated women. In the absence of data of naturally occurring variations in hormone levels of women treated with IA that allow us to interpret the results of hormone determinations under study, it is considered appropriate to include a placebo group to provide reference data. In this case, the placebo is a vaginal moisturizing gel.

It is estimated that a group of 11 women will allow the assessment of physiological fluctuations in hormone levels. Additionally, this sample size for the placebo group will provide 80% power and  $\alpha=0.05$  to differentiate between active and placebo (ratio 4:1) on the change in the vaginal maturation value, which is a secondary variable of the study that provides objective information about the effectiveness of treatment on vaginal atrophy (calculation based on the parameter data from the pivotal Blissel study and considering only the subgroup of women who had severe vaginal dryness: change VM active group 24.9 vs 0.6 points in placebo group, SD = 24.2).

The differentiation between active and placebo in the subjective parameters of efficacy (secondary) would be possible at the expense of a sample size noticeably superior. Since the evaluation of effectiveness is not primary but secondary in this study, it is not justified in this study to increase the sample for this reason.

In accordance with the above, the study would include 55 women. 44 will receive vaginal estriol gel and 11 with the placebo moisturizing gel). Taking into account 10% of dropouts, the sample to be considered is of 60 women (48 vaginal estriol gel and 12 placebo moisturizing gel). This is an unbalanced study but with an active: placebo ratio of 4:1, which will support an adequate patient randomization (blocks of 5).

10 additional women will be recruited in a first safety phase of the study (8 with vaginal estriol gel and 2 placebo moisturizing gel).

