### **8.2.6. Hormone levels**

All these analysis will be based on the ITT population.

The primary endpoint and one of the secondary endpoints are to evaluate the variation from baseline of FSH, LH, estriol, estradiol and estrone blood levels in patients treated with 0.005% estriol vaginal gel/placebo.

The variation of the levels of FSH, estriol, estradiol, estrone and LH after treatment with 0.005% estriol vaginal gel will be studied in each woman. The variation of levels between two arms will be analyzed using a non-parametric test (Mann-Whitney-Wilcoxon test) or an ANCOVA (if it must be adjusted by initial value).

Two determinations of FSH and LH before treatment with 0.005% estriol vaginal gel will be studied in each woman in order to study the intra-individual variation. Screening and baseline determinations will be used for this purpose.

Changes in hormone levels will be studied in each woman along the treatment (see sections 6.1 and 6.2).

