### **8.2.7. Efficacy**

The efficacy analysis will be evaluated in the ITT population.

The primary endpoint, the variation of FSH between week12 and baseline and comparing by arm will be analyzed using a non-parametric test (Mann-Whitney-Wilcoxon test).

An ANCOVA analysis will be used to corroborate the results obtained for the primary endpoint. The ANCOVA analysis will compare the variation of FSH 12 weeks adjusted by FSH basal between the two arms. This analysis will be performed if the relation between FSH 12 and FSH basal is lineal.

The variations in the intensities for each one of the symptoms and signs of the vaginal atrophy, after 3 and 12 weeks, in each treatment arm, will be compared using the non-parametric test Mann-Whitney-Wilcoxon.

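### The 80% FSH power in section 8.1 belongs to a within-arm test, but section 8.2.7 makes the primary FSH test a 44 vs 11 comparison of arms, whose power is not stated

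*Protocol*

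**What the plan says.** Section 8.1 takes its FSH inputs from a cited study of 10 women on aromatase inhibitors. That study gave no SD: "Although no figures are reported of the variability of those measurements, an estimation of the standard deviation can be made" as a quarter of the range of FSH values, 89/4 = 22.3. The section then says "it can be calculated that a sample size of 44 would provide 80% power to detect with an" alpha of 0.05 "a decrease of FSH levels from 75.7 to 66.0 mIU/ml assuming a standard deviation of 22.3". It names no test. The Summary repeats the paragraph.

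The placebo group is justified separately. It is to show natural hormone fluctuation, and its 11 women are said to give 80% power "to differentiate between active and placebo (ratio 4:1) on the change in the vaginal maturation value", a secondary variable. The evaluable numbers follow: "44 will receive vaginal estriol gel and 11 with the placebo moisturizing gel".

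Section 8.2.7 assigns the analysis: "The primary endpoint, the variation of FSH between week12 and baseline and comparing by arm will be analyzed using a non-parametric test", namely Mann-Whitney-Wilcoxon. An ANCOVA is to corroborate it if the relation to baseline is linear: "The ANCOVA analysis will compare the variation of FSH 12 weeks adjusted by FSH basal between the two arms". Section 8.2.6 also compares arms for the hormones: "The variation of levels between two arms will be analyzed using a non-parametric test".

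**The concern.** Section 8.1 describes a before-and-after fall in one treated group. Section 8.2.7 tests a difference between two groups, one of which has only 11 women. These are different tests with different standard errors, so a power for one does not carry over to the other. The protocol gives a between-arm power for a secondary variable but none for the primary endpoint.

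The direction of the hypothesis makes this matter. Section 1.6 expects no significant gonadotropin decline, so failure to reject is the result that favours the product. A reader who takes the 80% at face value would think a true fall of the sizing magnitude is missed one time in five. Under the protocol's own SD, the declared test would miss it about three times in four.

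A second weakness lies in the input. The 22.3 describes the spread of FSH levels between women, whereas both the paired test and the comparison of changes need the SD of within-woman change.

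**Working it through.** **Inputs from section 8.1.** Difference d = 75.7 - 66.0 = 9.7 mIU/ml; SD 22.3; alpha 0.05; evaluable 44 and 11. Two-sided testing is assumed here. The protocol states it only for the secondary analyses, but it is the reading that reproduces n = 44.

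**Step 1: reproduce the stated figure.** For a one-sample (paired) t-test the noncentrality is d/SD × √n = 9.7/22.3 × √44 = 2.885 on 43 df. Power is 80.5%; at n = 43 it is 79.6%. So 44 is the smallest n reaching 80%.

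**Step 2: try the other readings at SD 22.3.**
- One-sided paired test, n = 44: 88%
- Two-sample, 22 vs 22: 29%
- Two-sample, 44 vs 44: 52%
- Two-sample, 44 vs 11: 24.5%

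Only the two-sided within-arm reading fits.

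**Step 3: power of the declared primary comparison.** For 44 vs 11 the noncentrality is d / (SD × √(1/44 + 1/11)) = 9.7 / (0.3371 × SD) on 53 df. The SD of change is an assumption, varied from 10 to 22.3. If levels have SD 22.3 at both visits with correlation ρ, the SD of change is 22.3 × √(2(1 - ρ)). Mann-Whitney power is simulated (20,000 runs, normally distributed changes, no mean change on placebo).

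| SD of change | Corresponding ρ | Noncentrality | t-test | Mann-Whitney |
|---|---|---|---|---|
| 10 | 0.90 | 2.88 | 81% | 78% |
| 14.1 | 0.80 | 2.04 | 52% | 49% |
| 18 | 0.67 | 1.60 | 35% | 33% |
| 22.3 | 0.50 | 1.29 | 24.5% | 23% |

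Power reaches 80% only if the SD of change is about 10.1 or less (t-test) or 9.7 or less (Mann-Whitney). Using 22.3 as an SD of change amounts to assuming ρ = 0.5, which the protocol does not say.

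**Step 4: the corroborating ANCOVA.** The residual SD is 22.3 × √(1 - ρ²) on 52 df. Power is 31%, 43%, 56% and 83% at ρ = 0.5, 0.7, 0.8 and 0.9, against 24%, 37%, 52% and 81% for the t-test on change. It helps somewhat at low correlation but does not close the gap.

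**Step 5: no dropout.** With all 48 vs 12, t-test power is 84% at SD 10 and 26% at SD 22.3.

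**Step 6: what the comparison can show.** The difference detectable with 80% power (t-test) is 9.6 mIU/ml at SD 10 and 21.5 at SD 22.3. The 95% confidence interval half-width is 2.006 × 0.3371 × SD, which is 6.8 at SD 10 and 15.1 at SD 22.3.

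**Step 7: the maturation value, for comparison.** The difference is 24.9 - 0.6 = 24.3 with SD 24.2. At 44 vs 11 the power is 83%, so that between-arm claim holds.

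**The case against.** The best counter-argument uses the protocol's own account of the 10-patient study. Sections 1.4 and 8.1 give a fall of 9.7 mIU/ml, and section 1.4 calls the decline significant. With n = 10, a paired t-test reaches p < 0.05 only if the observed SD of change is at most 9.7 × √10 / 2.262 = 13.6. At 18 the p-value would be 0.12, and at 22.3 it would be 0.20. On this view the lower rows of the table are too pessimistic. The point has force, but it does not rescue the 80%: at SD 13.6 the between-arm power is still only about 52-55%. It also assumes a paired t-test that the protocol does not name, and it borrows a two-week change for a 12-week endpoint. An SD from 10 women is also imprecise: around an observed 13.6, the 95% interval runs from about 9 to 25. The range of 10 to 22.3 therefore stands.

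It can also be said that section 8.1 never claims 80% for the arm comparison, that placebo serves as reference data, that section 8.2.3 mentions a paired t analysis, and that the study calls itself exploratory. All of this is true, and it explains how the number arose. But section 8.2.3 is a general sentence under Patient Characteristics. Section 8.2.7 is the only place that assigns a test specifically to the primary endpoint, and that test is by arm.

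Finally, no passage says that a non-significant result will be taken as proof of no decline. That risk is inferred from the hypothesis and is not a stated decision rule.

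**Conclusion.** The concern holds. The arithmetic in section 8.1 is sound for a two-sided within-arm test, but the only FSH power in the protocol does not belong to the primary test declared in section 8.2.7. For a 9.7 mIU/ml difference at 44 vs 11, that test has 78-81% power if the SD of change is 10, 49-52% at 14.1, 33-35% at 18 and 23-25% at 22.3 (Mann-Whitney to t-test). The mismatch between the sections is certain. The size of the shortfall depends on an SD of change that the protocol does not give, on normally distributed changes and on two-sided testing. If the SD is about 10 or less, power is adequate. This should be corrected before the 80% is relied on, because it is a stated design figure in a study whose hypothesis is the absence of a decline.

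**What to change.** In section 8.1 and the Summary, once the sponsor confirms that this is the calculation behind n = 44, replace the power sentence with:

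> With 44 evaluable estriol patients, a two-sided one-sample (paired) test at 0.05 has about 80% power for a within-arm FSH fall of 9.7 mIU/ml if the SD of within-woman change is 22.3 mIU/ml (an assumption: range/4 of raw levels). The between-arm primary comparison in 8.2.7 (44 vs 11) was not sized for 9.7 mIU/ml. Its power for that difference is about 78-81%, 49-52%, 33-35% and 23-25% if the SD of change is 10, 14.1, 18 or 22.3 mIU/ml (Mann-Whitney to t-test). The detectable difference at 80% power is about 9.6 mIU/ml at SD 10 and 21.5 at SD 22.3 (t-test). A non-significant between-arm FSH result is not an 80%-powered finding of no decline.

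In section 8.2.7 add:

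> The FSH arm difference at week 12 will be reported with a 95% confidence interval.

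The interval is a new commitment. The Summary promises intervals only where possible, under Demographics and Baseline Characteristics. The other cost is a design figure that becomes conditional and less favourable. No patients, visits or tests are added, and the primary test stays as it is.

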## 8.2 Statistical and Analytical Plans

### 8.2.1 General Considerations

Statistical analysis of this study will be the responsibility of GEICAM (on behalf of the sponsor). The interpretation of study results will be the responsibility of the chief investigator of the study together with the sponsor.

Detailed methodology for summary and statistical analyses of the data collected in this study will be documented in a Statistical Analysis Plan (SAP), which will be dated and maintained by GEICAM (on behalf of the sponsor). This document may modify the plans outlined in the protocol; however, any major modifications of the primary endpoint definition and/or its analysis will also be reflected in a protocol amendment.

All the analysis will be performed using the statistical software SAS Enterprise Guide 5.1

#### 8.2.1.1 Patient Populations

**Intent to treat population (ITT):** The ITT population will include all patients who are randomized, with study treatment (Estriol gel vaginal 0.005% or placebo) assignment designated according to initial randomization.

The ITT population will be the primary population for evaluating patient characteristics, hormone levels, efficacy and the FSFI questionnaire.

**Per-protocol population:** a subset of the ITT population that received at least one dose of study drug and completed the study without any major protocol violations.

**Safety population:** will include all patients randomized in the study who received at least one dose of treatment, and they will be analyzed according to the actual treatment received. This population is for the safety analysis.

